1 SYNOPSIS

Title of Study: A Multicenter, Open-Label Retreatment Study of the Safety and Effectiveness of PN40082 for Lip Augmentation
Name of Sponsor: Prolenium Medical Technologies Inc.
Name of Finished Product: PN40082®
Device Composition: Hyaluronic acid gel with lidocaine (0.3% w/w)
Objectives: To evaluate the safety and efficacy of retreatment with PN40082 for lip augmentation.
Study Design: This is a multicenter, open-label clinical study of retreatment of subjects seeking lip augmentation who received treatment with either PN40082 or Restylane Silk in prior Protocol PRO 2018-02. Subjects meeting the inclusion/exclusion criteria will receive a single additional treatment with PN40082. Visits and telephone contacts will occur at: 
Visit 1 / Day 1 – baseline and treatment. This is the same visit as Visit 5 (Day 168) of Protocol PRO 2018-02.-Day 3 (±2 days) – Safety follow-up telephone call-Day 14 (±2 days) – Safety follow-up telephone call Visit 2 / Day 28 (±2 days) / Month 1 – Interim Visit Visit 3 / Day 56 (±4 days) / Month 2 – End of Study Visit 
-Day 168 (±7 days) / Month 6 – Safety follow-up telephone call Efficacy evaluations are: 
Lip Fullness Grading Scale (LFGS) - overall lip fullness considering both lips together, fullness of the upper lip, and fullness of the lower lipPerioral lines at rest severity scale (POL) - overall perioral lines at rest severity considering both lips together, perioral lines at rest severity of the upper lip, and perioral lines at rest severity of the lower lipPatient Global Aesthetic Improvement (pGAI)Investigator Global Aesthetic Improvement (iGAI) Safety will be assessed by monitoring adverse events (AEs) at all study visits. Other safety evaluations are lip function, lip sensation, lip texture, lip firmness, lip symmetry, and lip movement/function. Other evaluations are Investigator Ease of Use Assessment, Swelling Assessment, and Subject Satisfaction with Lips Assessment.
Number of Study Centers: Six (6) sites in the United States
Duration of Participation: Subjects will participate in the study for approximately 6 months from the time they sign the informed consent form (ICF) through the final contact

Duration of Study: The study will require approximately 20 months from the beginning to the end of the study (first subject signing the ICF to last contact with last subject)

Number of Subjects: Eligible subjects from the PRO 2018-02 study will be encouraged to be retreated. It is anticipated that the number of subjects will be less than the 158 subjects enrolled in the PRO 2018-02 study.

Inclusion Criteria:

1. In Protocol PRO 2018-02, met all inclusion/exclusion criteria; received study device, completed Visit 5 within the specified window; had LFGS score by the Blinded Evaluating Investigator at Visit 3/Month 2 within the specified visit window, and had no significant protocol violations that would affect the treatment evaluation.
2. If female and of childbearing potential, a negative urine pregnancy test at Visit 1/Day 1 and the subject agrees to use adequate contraception during the study period.
3. Willing to give written informed consent

Exclusion Criteria:

1. Women who are pregnant, lactating, or planning a pregnancy

Study Device

PN40082: a clear, colorless gel in 1.0 mL pre-filled syringes with 25 mg/mL of stabilized hyaluronic acid and lidocaine 0.3% w/w

Statistical Methods

Safety and efficacy results will be summarized descriptively for all subjects who receive retreatment in this study. Data will be summarized overall and also broken down by the treatment arm in PRO 2018-02.

Efficacy Analysis:

Change from baseline in this study and change from baseline in the prior controlled study will be summarized for LFGS and POL. Other efficacy variables include pGAI, iGAI, and Swelling Assessment at Visit 3/Month 2.

Safety Analysis:

Adverse events will be coded to system organ class and preferred terms using the Medical Dictionary for Regulatory Activities (MedDRA, Version 20 or higher).

Frequency and percentage of subjects reporting treatment-emergent adverse events (TEAEs) will be tabulated overall and for each treatment in PRO 2018-02 by preferred terms and further by severity and relationship to study device. In summaries of severity and relationship, subjects reporting more than one event in a treatment arm that are mapped to the same preferred term will be counted only once in that treatment arm under the strongest severity and relationship, respectively. In addition, visual-related TEAEs will be summarized separately by preferred term.

2 SCHEDULE OF ACTIVITIES

Visit Number (Month)	Visit 1 ^a	Phone Contacts	Visit 2 (Mo 1)	Visit 3 (Mo 2)	Phone Contact (Mo 6)	Unsched Visit
Scheduled Day(s)	Day 1	Day 3 & Day 14	Day 28	Day 56	Day 168	
Scheduling Window	± 7 days	± 2 days	± 2 days	± 4 days	± 7 days	
Informed consent	X					
Medical history/ demographics	X ^b					
Vital Signs	X					
Vision evaluations (Snellen visual acuity, confrontational visual fields, ocular motility) ^c	X		X	X		X ^d
Concomitant medication/ Treatment	X	X	X	X	X	X
Inclusion/exclusion criteria review	X					
Urine pregnancy test ^e	X					
Lip Fullness Grading Scale (LFGS) (overall, upper lip, and lower lip)	X		X	X		X ^d
Perioral lines at rest severity scale (POL) (overall, upper lip, and lower lip)	X		X	X		X ^d
Treatment with PN40082	X					
Investigator Ease of Use Assessment	X					
Patient GAI (pGAI)	X		X	X		X ^d
Swelling Assessment	X		X	X		X ^d
Investigator GAI (iGAI)	X		X	X		X ^d
Subject Satisfaction with Lips	X		X	X		X ^d
Lip function	X ^f		X	X		X ^d
Lip sensation	X ^f		X	X		X ^d
Lip texture	X ^f		X	X		X ^d
Lip firmness	X ^f		X	X		X ^d
Lip symmetry	X ^f		X	X		X ^d
Lip movement/function	X ^f		X	X		X ^d
Adverse event assessment	X	X	X	X	X	X
Subject Diary	Dispense		Collect			

Note: The timing of each visit is relative to Day 1, which is defined as the day the subject is treated.

- This is also Visit 5 of Protocol PRO 2018-02 and assessments performed at that visit do not need to be repeated.
- To be updated if/as needed for changes since Visit 1 of PRO 2018-02.
- To be performed prior to any treatment and repeated 30 minutes following any treatment and all follow-up visits.
- If/as needed
- For women of childbearing potential, to be completed prior to enrollment.
- To be performed prior to injections

4 LIST OF ABBREVIATIONS AND DEFINITIONS OF TERMS

Term	Definition
AE	adverse event
CFR	Code of Federal Regulations
CRF	case report form, paper or electronic
DCF	data correction form
EOS	end of study
FDA	Food and Drug Administration
GCP	Good Clinical Practice
ICF	informed consent form
ICH	International Council for Harmonisation
iGAI	Investigator Global Aesthetic Improvement
IRB	Institutional Review Board
IUD	intrauterine device
LFGS	Lip Fullness Grading Scale
MedDRA	Medical Dictionary for Regulatory Activities
OTC	over-the-counter
pGAI	Patient Global Aesthetic Improvement
PI	principal investigator
POL	Perioral Lines Severity Scale
SAE	serious adverse event
SAR	suspected adverse reaction
SOP	standard operating procedure
TEAE	treatment-emergent adverse event
VAS	visual analog scale

5 INTRODUCTION

PN40082 is a stabilized hyaluronic acid dermal filler with lidocaine. The purpose of this study is to evaluate the efficacy and safety of PN40082 in subjects who received one treatment 6 months earlier, with or without a subsequent touch-up treatment, for lip augmentation.

6 STUDY OBJECTIVES

To evaluate the safety and efficacy of retreatment with PN40082 for lip augmentation.

7 INVESTIGATIONAL PLAN

7.1 Overall Study Design

This is a multicenter, open-label clinical study of retreatment of subjects seeking lip augmentation who received treatment with either PN40082 or Restylane Silk in prior Protocol PRO 2018-02. Subjects meeting the inclusion/exclusion criteria will receive a single additional treatment with PN40082.

Visits and telephone contacts will occur at:

Visit 1 / Day 1 – baseline and treatment. This is the same visit as Visit 5 (Day 168) of Protocol PRO 2018-02.

-Day 3 (± 2 days) - Safety follow-up telephone call

-Day 14 (± 2 days) – Safety follow-up telephone call

Visit 2 / Day 28 (± 2 days) / Month 1 – Interim Visit

Visit 3 / Day 56 (± 4 days) / Month 2 – End of Study (EOS) Visit

-Day 168 (± 7 days) – Safety follow-up telephone call

Efficacy evaluations are:

Lip Fullness Grading Scale (LFGS) - overall lip fullness considering both lips together, fullness of the upper lip, and fullness of the lower lip

Perioral lines at rest severity scale (POL) - overall perioral lines at rest severity considering both lips together, perioral lines at rest severity of the upper lip, and perioral lines at rest severity of the lower lip

Patient Global Aesthetic Improvement (pGAI)

Investigator Global Aesthetic Improvement (iGAI)

Safety will be assessed by monitoring adverse events (AEs) at all study visits. Adverse events of special interest, including any changes in vision and any events attributable to an embolic or ischemic cause (e.g., skin infarction), will be monitored. Other safety evaluations are lip function, lip sensation, lip texture, lip firmness, lip symmetry, and lip movement/function.

Other evaluations are Investigator Ease of Use Assessment, Swelling Assessment, and Subject Satisfaction with Lips Assessment.

7.2 Beginning and End of Study

A subject is considered to be enrolled in the study when he/she has provided written informed consent.

A subject is considered to have completed the study after he/she has completed the Month 6 safety telephone call.

A subject is considered to have withdrawn after he/she has withdrawn consent or has been withdrawn under the conditions specified in [Section 7.3.3](#).

A subject is considered to have been lost to follow-up if he/she cannot be contacted by the investigator. The investigator will document efforts to attempt to reach the subject at least twice by telephone and will send a certified letter before considering the subject lost to follow-up. The end of participation for a subject lost to follow-up is documented as the date of the certified letter.

Each subject will be monitored for the occurrence of AEs, including serious adverse events (SAEs), starting immediately after treatment initiation. Each subject will be followed for safety monitoring until he/she is discharged from the study.

Follow-up procedures related to pregnancy, AEs, or SAEs may continue beyond the end of the study.

Each subject will participate in the study for approximately 6 months from the time he/she signs the ICF through the final contact. After determination of eligibility at Visit 1/Day 1, each subject will be treated with study device.

It is anticipated that the duration of this study will be 20 months from the beginning to the end of the study (first subject signing the ICF to last contact with last subject).

7.3 Study Population

7.3.1 Inclusion Criteria

Subjects must meet all of the following criteria to be eligible for the study:

1. In Protocol PRO 2018-02, the subject was in the per-protocol population, i.e., met all inclusion/exclusion criteria; received study device, completed Visit 5 within the specified window; had LFGS score by the Blinded Evaluating Investigator at Visit 3/Month 2, and had no significant protocol violations that would affect the treatment evaluation.
2. If female and of childbearing potential, a negative urine pregnancy test at Visit 1/Day 1 and the subject agrees to use adequate contraception during the study period
3. Willing to give written informed consent

7.3.2 Exclusion Criteria

Subjects who meet any of the following criteria will be excluded from the study:

1. Women who are pregnant, lactating, or planning a pregnancy

7.3.3 Subject Withdrawal Criteria

A subject may withdraw from the study at any time for any reason.

A subject will be withdrawn from the study if his/her safety or well-being is determined to be at risk. Withdrawal will be made at the discretion of the investigator or at the subject's request.

A subject must withdraw from the study for any of the following reasons:

- The subject or legal representative withdraws consent
- There is a significant protocol violation as determined by the Sponsor or medical monitor.

A subject may be withdrawn from the study for any of the following reasons:

- Lost to follow-up
- Investigator discretion

Withdrawal is permanent; after a subject has been withdrawn, he/she will not be allowed to enroll again.

If a subject is withdrawn from the study for any reason, the EOS or Early Termination procedures (Visit 3/Month 2) should be completed and any outstanding data and study device should be collected. Data, including the date and primary reason for withdrawal, must be documented on the EOS case report form (CRF) and source document.

If a subject withdraws from the study at any time due to an AE, the reason for withdrawal, the nature of the AE, and its clinical course must be fully documented. The investigator must strive to follow the subject until the AE has resolved, become clinically insignificant, is stabilized, or the subject is lost to follow-up. For any SAE, follow procedures provided in Section 7.9.7.

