7.4.2 Study Device Administration

All subjects in this study will receive one open-label treatment with PN40082. Subjects will maintain the unique subject number previously assigned in Protocol PRO 2018-02.

The subject should be positioned in a seated position and may be reclined to as much as 45°.

Any makeup should be removed with a gentle cleanser or a specific makeup remover product (such as Neutrogena Cleansing Makeup Remover Facial Wipes).

The non-vermillion areas of the upper and lower lips should be prepared by gentle washing with a surgical scrub product (Chlorhexidine, Technicare, etc.).

To prepare the syringes for use, the investigator should attach one of the needles included in the subject study device kit in a firm manner. The plunger should be gently depressed to express any unwanted air until a small droplet of implant material appears at the tip of the needle.

Study device is administered using only a needle provided in the subject study device kit. The needle is inserted at an approximate angle of 30° parallel to the surface of the skin or lip. For rhytids, study device should be injected into the mid-to-deep dermis. Study device should be injected into the submucosal layer for lip augmentation; care should be taken to avoid intramuscular injection. If study device is injected too superficially this may result in visible lumps and/or bluish discoloration.

Inject study device applying light to moderate, even pressure on the plunger. Avoid injecting quickly as rapid injection can result in increased pain. It is important that the injection is stopped just before the needle is pulled out of the skin to prevent material from leaking out or being too superficially implanted into the skin.

Only correct or augment to 100% of the desired volume effect. Do not overcorrect or overfill.

The needle may be replaced as needed to ensure subject comfort. Only needles provided in the subject study device kit may be used. Before needle replacement, the plunger should be withdrawn slightly and once the needle has been replaced, the plunger re-advanced to ensure that the new needle is prefilled with implant material prior to restarting injections.

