7.9.4 Pregnancy

Pregnancies occurring after administration of study device require immediate reporting. They must be reported within 24 hours after the investigator has become aware of the pregnancy. A pregnancy report will be completed and sent by fax to the Sponsor or designee within 24 hours of becoming aware of the pregnancy. The investigator will collect follow-up information regarding the outcome of the pregnancy and any postnatal sequelae in the infant that must also be reported to the Sponsor or designee. Upon awareness of the outcome of the pregnancy, the Principal Investigator or designee must forward a follow-up Pregnancy Report with any relevant information to the Sponsor or designee.

If the outcome of the pregnancy meets the criteria for immediate classification of an SAE (e.g., spontaneous abortion, stillbirth, neonatal death, or congenital anomaly), the investigator will report the event by faxing a completed SAE report form to the Sponsor or designee within 24 hours of being notified of the pregnancy report.

The subject should immediately be withdrawn from the study.

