5.2 Handling of Dropouts or Missing Data

All summaries will be generated using the available data without imputation for the missing values.

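### Required withdrawal from the study after a one-time Day 1 treatment ends planned collection of new-onset AEs before Day 168, so all-treated TEAE percentages can be biased low

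*Protocol*

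**What the plan says.** Protocol 7.3.3 introduces its mandatory list with "A subject must withdraw from the study for any of the following reasons". The list has two entries: withdrawal of consent, and "There is a significant protocol violation as determined by the Sponsor or medical monitor". It does not define a significant violation and does not mention pregnancy. Protocol 7.9.4 deals with pregnancy separately: "The subject should immediately be withdrawn from the study". SAP Table 14.1.2 has a discontinuation row for each of these reasons.

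On treatment, Protocol 7.4.2 states: "All subjects in this study will receive one open-label treatment with PN40082". On the length of safety observation, Protocol 7.2 says "Each subject will be followed for safety monitoring until he/she is discharged from the study" and "A subject is considered to have completed the study after he/she has completed the Month 6 safety telephone call". On what happens at withdrawal, Protocol 7.3.3 says "If a subject is withdrawn from the study for any reason, the EOS or Early Termination procedures (Visit 3/Month 2) should be completed"; Protocol 7.9.10 asks for the same procedures where possible.

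SAP Section 4 analyses every retreated subject. Footnote 1 of SAP Table 14.3.2.9 sets the subject-level denominator as all subjects who received the corresponding treatment. SAP 5.2 adds: "All summaries will be generated using the available data without imputation for the missing values". No rate adjusted for follow-up time is planned.

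**The concern.** In a study with repeated dosing, withdrawal may protect the subject by stopping treatment. Here nothing is left to stop after Day 1, so withdrawal removes only observation. One trigger is a judgement by the Sponsor or medical monitor in an open-label study, with no stated definition.

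Safety is half of the study objective, and the Day 168 call exists to pick up late events. Appendix 2 (Instructions for Use) itself warns of delayed-onset inflammatory papules after dermal fillers. If a subject leaves early and stays in the denominator, any later event goes uncounted and the subject is tabulated as though it had not happened.

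**Working it through.** **1. What stops at withdrawal and what continues**

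- Still collected: the AE, vision and lip assessments of the early-termination visit (Protocol 7.7.4).
- Still followed: an AE that caused the withdrawal (7.3.3, 7.9.5), SAEs until normal or stable (7.9.5, 7.9.7), and pregnancy outcome with postnatal sequelae (7.9.4).
- Permitted but not required: other follow-up of AEs or pregnancy beyond the end of the study (7.2, 7.9.5).
- Not required in any available text: the Day 168 call, or any other collection of new-onset AEs, after the termination contact. The opening part of 7.9.7 is not in the available text, so any rule there on SAE reporting after withdrawal could not be checked.

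**2. Follow-up lost per withdrawn subject**

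Treatment is Day 1 and the last contact is Day 168, so planned follow-up is 168 − 1 = 167 days.

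- Withdrawal at Day 28: 168 − 28 = 140 days; 140/167 = 84%.
- Withdrawal at Day 56: 168 − 56 = 112 days; 112/167 = 67%.

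These are shares of one subject's calendar time, not of events.

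**3. Effect on a subject-level percentage**

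The plan gives no figure to reproduce: it is descriptive and the sample size is not calculated. The following values are therefore assumptions: true 168-day incidence F = 5%, 20% or 50%; share withdrawn w = 1% to 10%; withdrawal day d = 28 or 56; the same risk in withdrawn and retained subjects.

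Observed incidence = (1 − w)F + wF(d), so the relative underestimate is w(1 − F(d)/F).

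- Constant hazard: F(d) = 1 − (1 − F)^(d/168).
- Mostly early onset: 90% of first onsets by Day 14, the rest uniform to Day 168, so F(d)/F = 0.9 + 0.1(d − 14)/154.
- Onset only after withdrawal: F(d) = 0, so the relative underestimate is w.

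Example with F = 20%, w = 5%, d = 28:

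- Constant hazard: F(28) = 1 − 0.8^(28/168) = 3.65%. Observed = 0.95 × 20% + 0.05 × 3.65% = 19.2%, a relative loss of 4.1%.
- Early onset: F(28)/F = 0.9 + 0.1 × 14/154 = 0.909. Observed = 19% + 0.05 × 20% × 0.909 = 19.9%, a relative loss of 0.45%.

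Range of relative underestimate over all F and d:

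| Share withdrawn | Mostly early onset | Constant hazard | Onset only after withdrawal |
|---|---|---|---|
| 1% | 0.07–0.09% | 0.6–0.8% | 1% |
| 3% | 0.22–0.27% | 1.8–2.5% | 3% |
| 5% | 0.36–0.45% | 2.9–4.1% | 5% |
| 10% | 0.73–0.91% | 5.9–8.3% | 10% |

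The largest absolute shortfall in the first two patterns is 3.9 percentage points (F = 50%, w = 10%, d = 28, constant hazard).

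**4. Rare late events**

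The synopsis expects fewer than 158 subjects, so 158 is used as a ceiling. For a late event with an assumed true risk of 1%, the chance of seeing at least one case is 1 − 0.99^n: 79.6% for n = 158, 77.9% for 150 and 76.0% for 142. With no cases, the one-sided 95% upper limit 1 − 0.05^(1/n) is 1.88%, 1.98% and 2.09%.

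**The case against.** The strongest reply is that little is lost. Observation is densest when most injection-site events would be expected: calls at Days 3 and 14, a two-week diary and the Day 28 visit. A subject withdrawn at the Day 56 visit misses one telephone call. The study makes no inferences, and the SAP tabulates discontinuations by reason and lists disposition and contact dates, so a reader can see how many left and when. All of this stands, and it limits the size of the problem. It does not recover an event that nobody asked about.

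A reader might also infer more than the documents support:

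- *That safety follow-up ends altogether.* It does not, given the termination assessments and the continued follow-up of AEs causing withdrawal, SAEs and pregnancy outcome.
- *That TEAE rates are biased low as a fact.* The number withdrawn is unknown and could be zero. The downward direction applies only to percentages with an all-treated denominator; SAP Tables 14.3.2.7, 14.3.2.8 and the event columns of 14.3.2.9 use events, or subjects with the event, instead. The no-imputation rule alone does not make anyone event-free; the fixed denominator does.
- *That the subjects lost are those at higher risk.* This is plausible: Protocol 7.4.2 ties certain injection practices to more local reactions, and Appendix 2 warns of inflammation from procedures such as laser or peels after treatment. But 7.3.3 does not say what a significant violation is, and nothing shows that those withdrawn would have more events.
- *That pregnancy and violation withdrawals are one mandatory rule.* They are worded differently and stand in different sections.

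**Conclusion.** The point holds in limited form. Withdrawal under 7.3.3 or 7.9.4 stops no exposure and leaves new-onset AEs between the termination contact and Day 168 without planned collection, while the subject stays in the denominator. The possible bias is downward. It is negligible if few are withdrawn or onset is early, and greatest for delayed events, where the relative loss equals the share withdrawn. The sizes rest on assumed incidence, withdrawal share, withdrawal day and onset pattern, and on equal risk in withdrawn and retained subjects; higher risk among the withdrawn would increase the loss. This is an inexpensive improvement to make, not a flaw that undermines the study.

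**What to change.** - In Protocol 7.3.3, replace mandatory study withdrawal for a significant violation with flagging or exclusion of the affected efficacy scores. Continue the safety contacts already scheduled, through the Day 168 call, unless the subject withdraws consent.
- Apply the same continued AE data collection to other withdrawals not based on consent, including those for pregnancy, safety or investigator discretion. This concerns data collection only and proposes no clinical rule.
- Reconcile 7.3.3, which does not list pregnancy, with 7.9.4 and SAP Table 14.1.2.
- In the SAP, report follow-up time, or TEAE incidence by onset period, beside the all-treated percentages.

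Cost: minor protocol and SAP wording, one or two added summaries, and a few more telephone contacts. Treatment is unchanged.
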